7.7 Definitions of significant toxicity

- 7.71 Toxicity will be measured per NCI-CTCAE version 5. For this protocol, significant toxicity will be defined as an adverse event occurring during the first 3 cycles of treatment that is possibly, probably, or definitely related as follows: NOTE: All significant non-hematologic toxicities must be resolved to a minimum of grade 1 for ongoing treatment at any cycle of treatment.
 - 7.711 Non-Hematological significant toxicities. Any Grade 3 or Grade 4 non-hematological toxicity that is possibly, probably or definitely attributable to the regimen of RSC+Pola+Ven is considered a significant toxicity, including the following:
 - Non-hematologic toxicity that causes a delay of >14 days in initiating cycle 2.
 - Any type of grade 3-4 hypersensitivity reaction (i.e.: allergic reaction, anaphylaxis, serum sickness, skin disorders, etc.), regardless of attribution, that necessitate discontinuation of study drug.
 - Any type of grade 3-4 immune related adverse event or immune system disorder including skin reactions.
 - Grade 3 or greater colitis and bowel perforation
 - Grade 3 ALT/AST elevation
 - Grade 3 or greater TLS

NOTE: The following events are exclusions and are NOT considered a significant toxicity for this protocol, regardless of attribution or specific type:

• Grade 3 nausea, vomiting, diarrhea, or oral mucositis with < 3 days

duration.

- Grade 3 fever.
- Grade 3 peripheral sensory neuropathy that is decreased by at least one grade within 7 days.
- Grade 3 hypophosphatemia, hypokalemia, hypocalcemia or hypomagnesemia responsive (i.e.: decreased by at least one grade) to oral supplementation within 7 days.
- Grade 3 hypertriglyceridemia that returns to < Grade 2 prior to the beginning of cycle 2.
- Grade 3 hyperglycemia that returns to < Grade 2 (with or without the use of insulin or oral diabetic agents) prior to the beginning of cycle 2.
- 7.713 Hematological significant toxicity. The following hematological toxicity possibly, probably or definitely attributable to the regimen of RSC+Pola+Ven is considered a significant toxicity:
 - Grade 4 neutropenia for > 7 days without growth factor support
 - Grade 4 febrile neutropenia
 - **NOTE:** Grade 4 non-febrile neutropenia will not be a significant toxicity but should warrant growth factor support on subsequent doses.
 - Platelet count < 25,000/uL on 2 separate days, or requiring a platelet transfusion on 2 separate days within a 7-day period

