8.0 Dosage Modification Based on Adverse Events

Dose modification guidelines are provided specifically for venetoclax, polatuzumab vedotin, rituximab, and rituximab/hyaluronidase human in the tables below. In addition, Venetoclax dose reductions will be discussed in Section 8.21.

If the patient requires a dose reduction, no dose re-escalation (e.g. no return to the baseline dose) is permitted.

Additional dose reductions may be employed at investigator discretion as clinically appropriate to ensure patient safety, and exact modification, timing, and reasons should be recorded.

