Infections and Infestations; AE: Hepatitis viral	Discontinue therapy and treat hepatitis		

Table 8.32: Guidelines for Management of Non-Hematologic Toxicities That Occur During Induction (cont.)

Event	Grade	Action to Be Taken	
Peripheral Neuropathy	Grade 4	Permanently discontinue polatuzumab vedotin and all other study treatment.	
	Grade 2	1. Delay study treatment. a	
	or 3	2. If improvement to Grade 1 within 21 days, resume study treatment for current and subsequent cycles as follows:	
		a. Resume rituximab or rituximab and hyaluronidase human at full dose	
		b. Resume venetoclax at current dose ^a	
		c. For patients who started at 1.8 mg/kg, resume polatuzumab vedotin at the permanently reduced dose of 1.4 mg/kg;	
Other non-hematologic toxicities (i.e., not described above), excluding alopecia, nausea, and vomiting	Grade 3 or 4	 dose of 1.4 mg/kg; For patients who have had no prior dose reductions: Withhold study treatment.^a If improvement to Grade 1 or baseline, resume rituximab and polatuzumab vedotin at full dose and resume venetoclax at next lower dose ^a for current and subsequent cycles perguidelines. For patients who have had one prior dose reduction: Grade 4 events Permanently discontinue study treatment. Grade 3 events Withhold study treatment.^a If improvement to Grade 1 or baseline, rituximab and polatuzumab vedotin at full dose and resume venetoclax at next lower dose ^a for current and subsequent cycles per guidelines. No more than two dose level reductions from the original dose of venetoclax are allowed during induction. For patients who have had two prior dose reductions: Permanently discontinue study treatment. 	
	Grade 2	 Withhold study treatment.^a If improvement to Grade 1 or baseline, resume rituximab and polatuzumab vedotin, and venetoclax at full dose. 	

IRR-infusion-related reaction; PML-progressive multifocal leukoencephalopathy; TLS-tumor lysis syndrome; ULN-upper limit normal.

^a Treatment delays apply to all events; dose modifications apply only to events that are considered to be related to any of the study treatment components. Toxicities that occur during the cycle and subside prior to the next cycle should not trigger the suggested dose modifications.

8.4 Toxicities during Maintenance Treatment provides guidelines for management of toxicities that occur during maintenance treatment.

Table 8.43: Guidelines for Management of Toxicities That Occur during Maintenance Treatment

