8.5 Management of Adverse Reactions for polatuzumab

Table 8.51 Management of Peripheral Neuropathy, Infusion-Related Reaction, and Myelosuppression

Table 8.51 Management of	Table 8.51 Management of Peripheral Neuropathy, Infusion-Related Reaction, and Myelosuppression				
Event	Dose Modification				
Grade 2–3 Peripheral Neuropathy	 Hold polatuzumab dosing until improvement to Grade 1 or lower. If recovered to Grade 1 or lower on or before Day 14, restart polatuzumab with the next cycle at a permanently reduced dose of 1.4 mg/kg. If a prior dose reduction to 1.4 mg/kg has occurred, discontinue polatuzumab. If not recovered to Grade 1 or lower on or before Day 14, discontinue polatuzumab. 				
Grade 4 Peripheral Neuropathy	Discontinue polatuzumab.				
Grade 1–3 Infusion- Related Reaction	 Interrupt polatuzumab infusion and give supportive treatment. For the first instance of Grade 3 wheezing, bronchospasm, or generalized urticaria, permanently discontinue polatuzumab. For recurrent Grade 2 wheezing or urticaria, or for recurrence of any Grade 3 symptoms, permanently discontinue polatuzumab. Otherwise, upon complete resolution of symptoms, infusion may be resumed at 50% of the rate achieved prior to interruption. In the absence of infusion related symptoms, the rate of infusion may be escalated in increments of 50 mg/hour every 30 minutes. For the next cycle, infuse polatuzumab over 90 minutes. If no infusion-related reaction occurs, subsequent infusions may be administered over 30 minutes. Administer premedication for all cycles. 				
Grade 4 Infusion- Related Reaction	 Stop polatuzumab infusion immediately. Give supportive treatment. Permanently discontinue polatuzumab. 				
Grade 3–4 Neutropenia ^{a,b}	 Hold all treatment until ANC recovers to greater than 1000/microliter. If ANC recovers to greater than 1000/microliter on or before Day 7, resume all treatment without any additional dose reductions. Consider granulocyte colony-stimulating factor prophylaxis for subsequent cycles, if not previously given. 				
Grade 3–4 Thrombocytopenia ^{a,b}	 Hold all treatment until platelets recover to greater than 75,000/microliter. If platelets recover to greater than 75,000/microliter on or before Day 7, resume all treatment without any additional dose reductions. 				
Infections and Infestations: Hepatitis Viral	Discontinue therapy and treat hepatitis				

^a Severity on Day 1 of any cycle.

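### For a patient with no prior dose reduction, Table 8.32 read literally resumes polatuzumab after severe infusion-related reactions for which Table 8.51 stops it permanently, and nothing says which table governs

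*Combined protocol and SAP*

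**What the plan says.** Section 8.0 introduces all the modification tables together: "Dose modification guidelines are provided specifically for venetoclax, polatuzumab vedotin, rituximab, and rituximab/hyaluronidase human in the tables below". It does not rank them.

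Table 8.32 (Section 8.3) covers non-hematologic toxicity during induction. Its last row is "Other non-hematologic toxicities (i.e., not described above), excluding alopecia, nausea, and vomiting". For Grade 3 or 4 the action depends on dose-reduction history:

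- The first branch is headed "For patients who have had no prior dose reductions". Treatment is withheld and then: "If improvement to Grade 1 or baseline, resume rituximab and polatuzumab vedotin at full dose and resume venetoclax at next lower dose".
- The second branch treats Grade 4 differently: "For patients who have had one prior dose reduction: Grade 4 events Permanently discontinue study treatment". Grade 3 in this branch again leads to withholding and, on recovery, polatuzumab at full dose.
- After two prior reductions, study treatment stops for good.

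Table 8.51 (Section 8.5) is specific to polatuzumab and lists infusion-related reactions by grade. In the Grade 1–3 row it says: "For the first instance of Grade 3 wheezing, bronchospasm, or generalized urticaria, permanently discontinue polatuzumab". Its Grade 4 row stops the infusion and ends polatuzumab permanently.

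Section 7.71 limits significant toxicity in the run-in to events at least possibly related to treatment, and the opening of 7.711 repeats this. One 7.711 bullet counts Grade 3–4 hypersensitivity reactions "regardless of attribution, that necessitate discontinuation of study drug".

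**The concern.** An investigator facing a severe infusion-related reaction can follow Table 8.32 and re-expose the patient to polatuzumab, or follow Table 8.51 and stop it. Either action complies with the protocol. The event can be life-threatening and the decision is made at the bedside. The branch with no prior dose reduction includes every patient at the first infusion. Beyond safety, sites could treat the same event differently, which blurs what the regimen was.

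The 7.711 wording is a separate matter. If 2 or more of the first 3 or 6 patients have significant toxicity, venetoclax may be de-escalated (7.61, 16.4). A rule that both requires and waives attribution leaves one of those two events open to dispute.

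**Working it through.** No arithmetic in the plan bears on this, so the check compares the tables branch by branch.

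**Does the residual row reach infusion-related reactions?** It takes in every non-hematologic event not described earlier in Table 8.32, apart from alopecia, nausea and vomiting. The earlier rows deal with treatment delays in general, tumor lysis syndrome, suspected PML, liver tests, viral hepatitis and peripheral neuropathy. Infusion-related reactions are neither described there nor excluded, so on a literal reading they are covered.

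**What does each table do with polatuzumab?**

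| Reaction | Prior dose reductions | Table 8.32, residual row | Table 8.51 | Result for polatuzumab |
|---|---|---|---|---|
| Grade 4 | 0 | Withhold, then full dose | Permanent stop | Opposed |
| Grade 4 | 1 | Permanent stop | Permanent stop | Agree |
| Grade 4 | 2 | Permanent stop | Permanent stop | Agree |
| First Grade 3 wheezing, bronchospasm or generalized urticaria | 0 | Withhold, then full dose | Permanent stop | Opposed |
| Same | 1 | Withhold, then full dose | Permanent stop | Opposed |
| Same | 2 | Permanent stop | Permanent stop | Agree |

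The tables are opposed in 1 of 3 Grade 4 branches and 2 of 3 Grade 3 branches: 1 + 2 = 3 of 6. In the three branches that agree on polatuzumab, Table 8.32 ends all study treatment while Table 8.51 names polatuzumab only.

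**Does a footnote resolve it?** Footnote a of Table 8.32 says that toxicities which clear before the next cycle should not prompt the dose modifications. An acute reaction that settles quickly would then leave doses unchanged under Table 8.32, which widens the gap from Table 8.51.

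**Is precedence stated anywhere?** Section 8.0 states none, and neither table refers to the other. Nor does Table 8.32 leave polatuzumab events to Table 8.51. Both rule on Grade 2–3 peripheral neuropathy, and differently: Table 8.32 allows 21 days for recovery, while Table 8.51 ends polatuzumab if recovery has not come by Day 14.

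**Section 7.711.** Take a Grade 3–4 hypersensitivity reaction judged unrelated that forces discontinuation. Under 7.71 and the opening of 7.711 it does not count; under the bullet it does.

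**The case against.** The strongest reply is that a specific table displaces a residual one. Table 8.51 sits in a section on polatuzumab reactions and names infusion-related reactions by grade, whereas Table 8.32 reaches them only through a catch-all. Many investigators would turn to Table 8.51. That is a sensible habit, but the protocol does not state it, and the overlapping neuropathy rows show that it cannot be presumed.

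A second reply is that a row may be missing. The legend of Table 8.32 defines IRR although no such row appears, and the table text is visibly damaged in places. A row lost in conversion from PDF cannot be ruled out. This reply stands as a condition on the point.

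A reader might also infer more than the documents support:

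- **That most patients will meet the contradiction.** The 80% and 40% figures in Section 15.49b concern rituximab infusions and carry no Grade 3–4 share. Section 1.231 does not list infusion reactions among the Grade 3 or higher events seen in at least 5% of patients on single-agent polatuzumab or in GO27834.
- **That run-in counting of related reactions turns on which table is used.** It does not. The opening of 7.711 already counts any related Grade 3 or 4 non-hematologic toxicity, and infusion reactions are not among the listed exceptions.
- **That rituximab reactions are governed only by the residual row.** Sections 15.44 and 15.49b give slow, stop and restart advice, mostly ungraded, and Table 7.2a requires a tolerated full IV dose before the subcutaneous form.
- **That milder reactions conflict in the other direction.** Table 8.51 says "infusion may be resumed at 50% of the rate achieved prior to interruption", but only after symptoms resolve completely. Table 8.32 withholds at Grade 2 until recovery to Grade 1 or baseline. The two can be read together.
- **That the primary analysis is compromised.** Under 16.11 and 16.311, evaluability does not depend on staying on polatuzumab.

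**Conclusion.** The contradiction is real in a limited form. On a literal reading, the tables give opposite polatuzumab instructions in 3 of 6 combinations of reaction and dose-reduction history, including both combinations with no prior reduction. This rests on two assumptions: that the residual row means what it says, and that no infusion-reaction row of Table 8.32 has been lost. How many patients would be affected cannot be estimated from the documents. The attribution mismatch in 7.711 also stands; it affects only hypersensitivity reactions judged unrelated that lead to discontinuation. Because the event is potentially life-threatening and the remedy is wording, the tables should be reconciled. No view is taken here on which clinical rule is right.

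**What to change.** First check the source version of Table 8.32 for an infusion-reaction row. If there is one, compare it with Table 8.51 and reconcile any difference.

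If there is none, add infusion-related and hypersensitivity reactions to the events excluded from the residual row, and point from there to a single governing rule. The study chair and the drug supplier should set the content of that rule.

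In 7.711, reword the hypersensitivity bullet so that it agrees with 7.71 on attribution, or state in 7.71 that the bullet is a deliberate exception.

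The cost is a wording amendment to Tables 8.32 and 8.51 and to the significant-toxicity definition (7.71 and 7.711), with no added patients, visits or tests.

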General guidance for treatment delays and discontinuation	 If study treatment is withheld for 21 days because of a toxicity that is attributable to study treatment, permanently discontinue study treatment. When a treatment cycle is delayed because of toxicity resulting from any component of the regimen, all study treatment should be held and resumed together to remain synchronized. 		
TLS	 Withhold study treatment.^a Correct electrolyte abnormalities, monitor renal function and fluid balance, and administer supportive care, including dialysis as indicated. If symptoms have resolved completely, resume rituximab and hyaluronidase human and polatuzumab at full dose and resume venetoclax at current dose. During venetoclax ramp-up, if venetoclax was withheld for 7 days or less, resume venetoclax at same dose level or at one lower dose level, as determined by the investigator (based on risk assessment, including tumor burden status). Refer to Table 8.21 for dose reduction steps. During venetoclax ramp-up, if venetoclax was withheld for more than 7 days, the dose must be resumed at one lower dose level, with the exception of the first dose (20 mg). Refer to Table 8.21 for dose reduction steps. If resolved within 24 to 48 hours of last dose, resume venetoclax at the same dose. For any blood chemistry changes requiring more than 48 hours to resolve, resume at a reduced dose. Refer to Table 8.21 for dose reduction steps. For any events of clinical TLS, resume at a reduced dose following resolution. Refer to Table 8.21 for dose reduction steps. 		
New-onset neurologic manifestations suggestive of PML AST, ALT, or bilirubin	 Withhold study treatment.^a Consult with a neurologist if PML is suspected. If PML is ruled out, resume rituximab and hyaluronidase human, polatuzumab vedotin and venetoclax at current dose. If PML is confirmed, permanently discontinue study treatment. 		
increase: Grade 3 (or 10x ULN for patients with liver involvement)	 If improvement to Grade 1, resume rituximab and polatuzumab vedotin at full dose and resume venetoclax at next lower dose for current and subsequent cycles per guidelines in Table 8.21. No more than 2 dose level reductions from original dose of venetoclax are allowed during induction. Patients who have had two prior dose reductions should be permanently discontinued. Refer to Table 8.21 for dose reduction steps. Permanently discontinue study treatment for life-threatening liver toxicity. 		

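### Table 8.32's Grade 2 row for other non-hematologic toxicities resumes polatuzumab and venetoclax at full dose with no branch for earlier reductions, which read literally contradicts Section 8.0's ban on re-escalation

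*Combined protocol and SAP*

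**What the plan says.** Section 8.0 sets a general rule before any of the dose tables: "If the patient requires a dose reduction, no dose re-escalation (e.g. no return to the baseline dose) is permitted". It names no drug and gives no exception.

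Table 8.32 (Section 8.3) covers non-hematologic toxicity during induction. Its resumption instructions are:

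- **Other toxicities, Grade 2:** "If improvement to Grade 1 or baseline, resume rituximab and polatuzumab vedotin, and venetoclax at full dose". There is no branch for earlier reductions.
- **Other toxicities, Grade 3 or 4, no prior reduction:** "If improvement to Grade 1 or baseline, resume rituximab and polatuzumab vedotin at full dose and resume venetoclax at next lower dose".
- **Other toxicities, Grade 3, one prior reduction:** "If improvement to Grade 1 or baseline, rituximab and polatuzumab vedotin at full dose and resume venetoclax at next lower dose".
- **AST, ALT or bilirubin increase:** "If improvement to Grade 1, resume rituximab and polatuzumab vedotin at full dose and resume venetoclax at next lower dose".
- **TLS:** "resume rituximab and hyaluronidase human and polatuzumab at full dose and resume venetoclax at current dose".
- **PML ruled out:** "If PML is ruled out, resume rituximab and hyaluronidase human, polatuzumab vedotin and venetoclax at current dose".
- **Neuropathy, Grade 2 or 3:** "resume polatuzumab vedotin at the permanently reduced dose of 1.4 mg/kg", with venetoclax at its current dose.

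Footnote a to the table says that toxicities which subside before the next cycle should not trigger the suggested modifications.

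**The concern.** A patient can reach the Grade 2 row after a reduction of either drug. Section 8.0 says the reduced dose must stay. The row says full dose, does not mention earlier reductions and does not point back to Section 8.0. The Grade 3 or 4 row in the same block does branch on none, one or two prior reductions, so the missing branch is conspicuous.

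The stake is dosing safety and consistency between sites. A site dosing from the row could put a patient already reduced for toxicity back on the unreduced dose. A site dosing from Section 8.0 would not. Both could cite the protocol.

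**Working it through.** No trial figure needs reproducing. The check is a comparison of texts plus three dose ratios.

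**1. Can a patient arrive at these rows already reduced?** Yes.

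- Venetoclax: a Grade 3 event in the Other block lowers it one step for current and subsequent cycles. Table 8.21 gives the steps from 400 mg as 300 mg, then 200 mg.
- Polatuzumab: Grade 2 or 3 neuropathy lowers it from 1.8 to 1.4 mg/kg, called permanent in both Table 8.32 and Table 8.51.
- Both drugs: a second Grade 3 or 4 hematologic event lowers each by one level (Table 8.31). That table refers to Table 8.21 for the steps, and Table 8.21 lists venetoclax only, so the reduced polatuzumab level on this route is not defined.

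**2. A worked sequence.** A patient on venetoclax 400 mg has a related Grade 3 event in the Other block and drops to 300 mg. In a later cycle the patient has a related Grade 2 event that has not subsided by the next cycle. On recovery, the Grade 2 row read literally returns venetoclax to 400 mg. Section 8.0 keeps it at 300 mg.

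**3. Size of the step if the row is followed literally.**

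| Drug and earlier reduction | Ratio | Increase |
|---|---|---|
| Venetoclax, one step | 400 / 300 = 1.333 | +33% |
| Venetoclax, two steps | 400 / 200 = 2.0 | 2-fold |
| Polatuzumab, neuropathy | 1.8 / 1.4 = 1.286 | +29% |

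The venetoclax figures assume the 400 mg starting level. The polatuzumab figure would carry over to the hematologic route only on the assumption that the undefined reduced level is also 1.4 mg/kg.

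**4. Which rows conflict, and when?**

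- *Other, Grade 2:* conflicts for venetoclax or polatuzumab after any earlier reduction of that drug.
- *AST/ALT/bilirubin:* the polatuzumab wording is unconditioned and conflicts after an earlier polatuzumab reduction. Venetoclax goes down, so there is no conflict there.
- *Other, Grade 3, one prior reduction:* conflicts only if that prior reduction included polatuzumab. If only venetoclax was reduced, polatuzumab is still at 1.8 mg/kg and the row is correct.
- *TLS:* conflicts only if polatuzumab was reduced earlier. That is unlikely, because Section 15.17 places the TLS risk in the first 5 weeks.

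**5. What do other sections suggest was intended?** That reductions last. Section 7.3, note 3, carries a reduced venetoclax dose into maintenance. Table 8.43 lowers venetoclax for a Grade 2 non-hematologic event in maintenance. The heading of Section 8.2 mentions re-escalation, but the section supplies no step that would permit it.

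**The case against.** The strongest reply is that Section 8.0 already governs. It introduces the tables as guidelines, footnote a calls their contents suggested modifications, and a flat prohibition at the head of the section need not be repeated in each row. On that view *full dose* means no further reduction for this event, a natural phrase when it is shared with rituximab, which has no reduction steps. For polatuzumab the reply is stronger still: Section 8.0 and the neuropathy rows of Tables 8.32 and 8.51 all point against a return to 1.8 mg/kg. Much of this stands. Applying Section 8.0 as the controlling rule prevents the harm. What the reply lacks is any text that defines *full dose* this way or ranks Section 8.0 above the tables.

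A reader might infer from the TLS row, which sets *full dose* for polatuzumab beside *current dose* for venetoclax, that *full dose* cannot mean the existing dose. That is too strong. TLS risk falls in ramp-up, when venetoclax has only a step dose, so the contrast may reflect ramp-up and nothing more. The PML row, which uses *current dose* for all the drugs, is better evidence: it shows that clearer wording was available.

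A reader might also infer that the Grade 3 and Grade 2 rows give opposite orders. They apply to different events at different times, and no single event receives both. The difficulty is that the later instruction, read literally, undoes the earlier one.

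Footnote a limits how often the rows apply. It does not say at what dose a previously reduced patient resumes.

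**Conclusion.** The contradiction is real, and clearest in the Grade 2 row for other non-hematologic toxicities. Read literally, that row reverses an earlier reduction by +33% or 2-fold for venetoclax (400 mg start) and by +29% for polatuzumab after neuropathy. The AST/ALT/bilirubin row repeats the problem for polatuzumab. The Grade 3 row after one prior reduction and the TLS row add little.

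The documents do not support saying that the protocol sets out to re-escalate patients. The Grade 2 row is silent on earlier reductions, and the surrounding text points to their being lasting. Nor do they allow an estimate of how many patients would be affected. Exposure is limited by Section 8.0, where it is applied, and by footnote a.

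This is a defect in dosing instructions. It does not affect the endpoint, decision rule, sample size or analysis. It deserves correction because the text can lead two sites to dose the same patient differently and the remedy is nearly free.

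**What to change.** **Grade 2 row, other non-hematologic toxicities.** Keep rituximab at full dose. For polatuzumab and venetoclax, replace *full dose* with: *the dose level in effect before the interruption (no re-escalation, per Section 8.0); during venetoclax ramp-up, after an interruption of more than 7 days, venetoclax resumes one dose level lower, except at 20 mg*. The ramp-up clause is needed because the TLS row of Table 8.32 and Appendix III already require that step down after a long interruption; without it the new wording would create a fresh conflict.

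**AST/ALT/bilirubin row.** For polatuzumab only, replace *full dose* with *the dose level in effect before the interruption*.

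**Other Grade 3 after one prior reduction, and TLS.** Make the same polatuzumab change for consistency. Leave their venetoclax instructions and the rituximab wording as they are.

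The cost is protocol wording in four table rows. No extra patients, procedures or analyses are needed.

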Any patient who, at any dose, develops clinically significant electrolyte abnormalities must have his or her subsequent venetoclax dose withheld until the electrolyte abnormalities resolve. Patients who develop electrolyte abnormalities should undergo aggressive management and further monitoring per Appendix II, Recommendations for Initial Management of Electrolyte Imbalances and Prevention of Tumor Lysis Syndrome. Any time during the ramp-up period, if venetoclax was withheld for 7 days or less, the patient may resume venetoclax at the same dose level or at one lower dose level as determined by the investigator based on a risk assessment (including tumor burden status). The dose must be resumed at one lower dose-level if interruption lasted more than 7 days, with the exception of the initial dose level of 20 mg (400 mg \rightarrow 200 mg, 200 mg \rightarrow 100 mg, 100 mg \rightarrow 50 mg, 50 mg \rightarrow 20 mg). All patients must receive the intended dose for at least 7 days before increasing to the next ramp-up dose.

For patients who are at high risk of TLS:

Hospitalized patients should receive TLS prophylaxis as described above for initial venetoclax
dosing. Nephrology (or acute dialysis service) must be consulted/contacted on admission (per
institutional standards) to ensure emergency dialysis is available and the appropriate staff are
aware and prepared to handle any necessary intervention for TLS. Telemetry should also be
considered.

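### The TLS row of Table 8.32 gives conflicting venetoclax restart doses, and footnote a adds to the ambiguity

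*Combined protocol and SAP*

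**What the plan says.** The TLS row of Table 8.32 (Section 8.3) first tells the site to hold study treatment, then gives several restart rules.

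Three of them lower the venetoclax dose:
- Clinical TLS: "For any events of clinical TLS, resume at a reduced dose following resolution".
- Slow laboratory recovery: "For any blood chemistry changes requiring more than 48 hours to resolve, resume at a reduced dose".
- Long hold in ramp-up: "if venetoclax was withheld for more than 7 days, the dose must be resumed at one lower dose level". The first dose of 20 mg is excepted.

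Three of them keep it, or may keep it:
- "If symptoms have resolved completely, resume rituximab and hyaluronidase human and polatuzumab at full dose and resume venetoclax at current dose".
- During ramp-up, "if venetoclax was withheld for 7 days or less, resume venetoclax at same dose level or at one lower dose level", as the investigator judges.
- "If resolved within 24 to 48 hours of last dose, resume venetoclax at the same dose".

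For the size of a reduction the row refers to Table 8.21. Appendix III repeats the rule for long ramp-up holds, "The dose must be resumed at one lower dose-level if interruption lasted more than 7 days", and lists its own steps, beginning with 400 mg to 200 mg.

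Footnote a to Table 8.32 states: "Toxicities that occur during the cycle and subside prior to the next cycle should not trigger the suggested dose modifications". In the TLS row its marker is on the instruction to hold treatment and on none of the restart bullets.

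**The concern.** A patient with clinical TLS during ramp-up can meet several of these bullets at once, and they do not lead to the same dose. Neither the row nor Sections 8.0 and 8.2, Table 8.44 or Appendices II to IV ranks them or says how footnote a relates to them.

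What is at stake is the dose at re-exposure. Section 15.17 treats TLS as a known risk of venetoclax, notably in MCL, and places that risk in the five weeks of ramp-up. Two sites could both comply and restart similar patients at different doses. The hold itself is not in doubt: Appendix III keeps venetoclax stopped until electrolyte abnormalities resolve.

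**Working it through.** No formula of the statistical design enters here. The check sets the rules side by side and adds calendar arithmetic.

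**Inputs.** Ramp-up of 20, 50, 100, 200 and 400 mg in successive weeks (Table 7.2b); 21-day induction cycles (Section 7.2); reduction steps (Table 8.21); ramp-up step-backs (Appendix III); a 3-day window either side of day 1 (Table 7.2a, note 2); TLS frequency (Section 15.17); 46 evaluable patients (Section 16.22).

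**1. One assumed patient.** The 200 mg step falls on study day 22. Clinical TLS is found on day 23, and symptoms and chemistry have resolved by day 26. The hold is 26 − 23 = 3 days, or 72 hours. One step below 200 mg in Table 8.21 is 100 mg.

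| Text | Restart dose |
|---|---|
| Clinical-TLS bullet | 100 mg |
| More-than-48-hour bullet | 100 mg |
| Symptoms-resolved bullet | 200 mg |
| 7-days-or-less bullet | 200 or 100 mg |
| Footnote a, taken literally | 200 mg |

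Strike the last line and the disagreement remains, so the row itself is the main source. Had the event resolved within 48 hours of the last dose, the 24-to-48-hour bullet would give 200 mg, against 100 mg from the clinical-TLS bullet.

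**2. Ramp-up hold of more than 7 days.**

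| Dose at hold | Table 8.21, one step down | Appendix III |
|---|---|---|
| 400 mg | 300 mg | 200 mg |
| 200 mg | 100 mg | 100 mg |
| 100 mg | 50 mg | 50 mg |
| 50 mg | 20 mg | 20 mg |

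The sources differ at one of the four levels, by 300 − 200 = 100 mg. A 300 mg dose is not a ramp-up level in Table 7.2b.

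**3. Can the footnote's condition be met?** The steps fall on study days 1, 8, 15, 22 and 29. The next day 1 is day 22 for the first three and day 43 for the last two. Days from step to next day 1:
- 20 mg: 22 − 1 = 21
- 50 mg: 22 − 8 = 14
- 100 mg: 22 − 15 = 7
- 200 mg: 43 − 22 = 21
- 400 mg: 43 − 29 = 14

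If the next day 1 is given 3 days early, these become 18, 11, 4, 18 and 11. An event must arise and resolve inside the gap. The patient in step 1 does so with 43 − 26 = 17 days to spare. Room is tightest at 100 mg, and at 20 mg Table 8.21 has no lower dose. Section 7.2 starts the ramp-up on day 7 rather than day 8; one day does not alter the result. The documents give no detection window for clinical TLS (the window in Appendix IV is for laboratory TLS), so these gaps show what is possible, not how often it happens.

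**4. How many patients.** Section 15.17 puts TLS at 1% to under 10%. If that range applies here, 46 × 0.01 = 0.46 and 46 × 0.10 = 4.6, so about 0.5 to under 4.6 patients. That section does not separate clinical from laboratory TLS, so patients who meet conflicting bullets may be fewer.

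**The case against.** The strongest reply is that a sensible reader can reconcile the text. The symptoms-resolved bullet can be read as the default and the clinical-TLS bullet as a specific exception covering every such event. The footnote marker points the same way. In the neuropathy and other non-hematologic rows it is attached to the venetoclax restart dose, but in the TLS row only to the hold. The footnote sentence also appears under Table 8.31, so it looks generic. Taken literally, it would cancel most of the reductions the row sets out, which is unlikely to be intended. Section 8.0 lets investigators reduce further, and the rule for holds of more than 7 days is mandatory both in the row and in Appendix III.

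Most of this stands. A reader might infer that footnote a overrides the row and that the protocol therefore permits a full-dose restart after clinical TLS. The marker placement and the specific wording of the row tell against that as the intended meaning. The footnote is a secondary source of doubt.

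Three things remain. The 7-days-or-less bullet is also specific, to ramp-up, and it leaves the dose to the investigator, so reading the specific over the general does not rank it against the clinical-TLS bullet. Discretion to reduce is not a duty to reduce. And nothing in this reply settles 300 mg against 200 mg.

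**Conclusion.** The point holds as a conflict among stated dosing rules. For clinical TLS in ramp-up the row can yield a reduced dose, the current dose, or a choice between them. For a hold of more than 7 days at 400 mg, two sources name different doses. Footnote a deepens the ambiguity because its wording makes no exception for TLS, although most careful readers would still reduce.

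The reach is small: about 0.5 to under 4.6 of 46 patients, assuming that the frequency in Section 15.17 carries over to this combination and population. It still deserves correction, because it concerns restart after a recognized toxicity in MCL and the remedy is short.

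A reader might also infer that the trial's conclusions are exposed. The documents do not support that. The 15% versus 35% test, the 46 patients and the decision rules do not depend on the restart dose after TLS.

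**What to change.** Make three short changes.

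1. Add to footnote a of Table 8.32: this exemption does not apply to venetoclax reductions in the TLS row. Leave it unchanged for other toxicities.
2. State in the TLS row that the clinical-TLS and more-than-48-hour bullets take precedence over the current-dose and 7-days-or-less bullets.
3. Give one restart level for a hold of more than 7 days at 400 mg during ramp-up: 200 mg, as in Appendix III. It is the lower of the two and is itself a ramp-up level.

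Do not add a rule that ramp-up step-backs are left out of the count of prior dose reductions unless the sponsor also exempts them from two other provisions. Section 8.0 bars re-escalation after a reduction, and note 3 of Section 7.3 carries an induction reduction into maintenance. Appendix III requires at least 7 days at a dose before the next increase, but does not expressly say that a patient who has stepped back may climb again.

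The cost is a few sentences, with no change to sample size, visits or data collection. The downside is a few more venetoclax reductions after TLS. Under Section 8.0 these could be lasting: a step back to 100 mg in week 4 could hold through maintenance. The sponsor should therefore decide on that exemption when making the change.
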